8.2 Method of Treatment Assignment

Patients in Phase 1 will be randomized. There is no randomization in Phase 2 and patients will be enrolled sequentially.

The study design for Phase 1 combines randomization and dose escalation. Randomization will be balanced for every 6 patients and stopped when the MTD/MAD is determined for either the QD or BID group. Patient enrollment will be on hold after 6 patients and resume when the next dose level is determined for both QD and BID groups. This process will continue for every 6 patients until MTD/MAD is determined for one of the dosing schemes, and randomization will be stopped. Then patient enrollment will resume and be on hold for every 3 patients until the

MTD/MAD is determined for the other dosing scheme. Patients who discontinue for reasons other than DLTs will be replaced.

8.3 Analysis Populations

Two analysis populations have been defined for each cohort as follows:

- The **Evaluable Population** consists of all patients in Phase 2 who are enrolled, complete at least 1 cycle of pozotinib treatment, and is evaluable for tumor response based on RECIST, Version 1.1 criteria. The efficacy data will be analyzed using the Evaluable Population.
- The **Safety Analysis Population** includes all patients who signed Informed Consent, enrolled, and received at least 1 dose of pozotinib. All demographics, Baseline characteristics, and safety data will be analyzed using the Safety Analysis Population.

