The total sample size for this study is approximately 76 patients. Phase 1 is a dose finding study using “3+3” design to determine the MTD/MAD in each dosing group (QD or BID). Up to 18 patients (up to 3 dose levels, up to 6 patients each level) will be included for DLT evaluation in each dosing group for a total of 36 patients in Phase 1. Patients who discontinue from the study before completing Cycle 1 treatment for reasons other than DLTs are not qualified for DLT evaluation and will be replaced.

A total of 40 patients (20 patients each in EGFR and HER2 mutation cohorts) will be enrolled in the dose confirmatory group in Phase 2 to confirm the activity in the identified pozotinib dose and schedule. The sample size of 20 patients in each mutation cohort in Phase 2 will provide a width for 95% confidence interval of 0.424 for the expected ORR of 30%.

Efficacy Analysis:

The primary efficacy variable ORR will be analyzed descriptively along with the 95% CI for each cohort. The determination of the ORR will be based upon radiographic assessment by the site’s Principal Investigator using RECIST Version 1.1. The secondary outcomes, DCR, DoR, and PFS, will be analyzed using descriptive statistics, for each cohort, and with 95% CI for DCR and Kaplan-Meier plot for DoR and PFS.

Analysis Populations:

The following analysis populations have been defined for each cohort:

[figure not shown]
- The **Evaluable Population** consists of all patients in Phase 2 who are enrolled, complete at least 1 cycle of pozotinib treatment, and are evaluable for tumor response based on RECIST, Version 1.1 criteria. The efficacy data will be analyzed using the Evaluable Population.
- The **Safety Analysis Population** includes all patients who signed Informed Consent, enrolled, and received at least 1 dose of pozotinib. All demographics, Baseline characteristics, and safety data will be analyzed using the Safety Analysis Population.

Safety and Tolerability:

The following variables will be summarized and analyzed descriptively for each cohort: number of completed cycles; number and percentages of patients with TEAEs, SAEs, TEAEs leading to study drug discontinuation, TEAEs related to the study drug; and the severity of TEAEs based on the grading by CTCAE, Version 5.0.

[figure not shown]
Protocol Version/Date: Amendment 2/04 Mar 2020

Study Design Diagram

Note: Phase 2 will start once the dose and dosing schedule have been determined in Phase 1.

Dose-Finding Diagram

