Cohort 1 enrolled a total of 115 patients who received 16 mg/day of pozotinib. The Intent-to-Treat analysis showed that 17 patients had a response (by RECIST) and 62 patients had stable disease for a 68.7% disease control rate (DCR). The confirmed objective response rate (ORR) was 14.8% (95% CI; 8.9%-22.6%). The median duration of response was 7.4 months. The best change in target lesion dimensions from Baseline is presented in **Figure 9**. The safety profile was at the high end of expected toxicities but in-line as to type of AE with other second-generation EGFR tyrosine kinase inhibitors. Permanent drug discontinuation related to AEs was seen in only 10% of patients but temporary drug interruption was seen in 88% of patients and dose reduction was seen in 68% of patients as permitted by protocol.

Figure 9 Best Percent Change in Sum of Target Lesion Dimension from Baseline

This study is being conducted to evaluate the safety of pozotinib in Japanese patients, a dose-escalating study beginning at 8 mg pozotinib QD and 4 mg BID is being conducted. Pharmacokinetic modeling of the 8 mg BID and 16 mg QD doses (the highest potential doses in the study), shows that BID dosing decreases fluctuations (i.e., difference between peak and trough concentrations) compared to QD dosing with a lower C_{max} (Figure 10) and the predicted AUC is expected to be similar for equivalent total daily doses. In Study HM-PHI-101, the 8-mg QD dose was well-tolerated in Phase 1 patients. In addition, activity and safety of BID dosing with pozotinib has not been previously investigated.

Figure 10 Simulated Poziotinib Plasma Concentrations Following QD and BID Dosing

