5.3.6 Treatment Period - Telephone Contact (Both Phases)

Cycle 1, Day 22 (± 2 days)

Cycle 2 - Days 8, 15, and 22 (± 2 days)

Cycles 3+ - Day 15 (± 2 days)

- Adverse event assessment using NCI CTCAE, Version 5.0
- Concomitant medications

5.3.7 Treatment Period Office Visit – Cycle 2+, Day 1

- Weight
- Physical examination
- Vital Signs
- Resting O₂ Saturation
- ECOG Performance Status assessment
- Pregnancy test in women of childbearing potential
- Complete blood count with 5-part differential
- Serum chemistry, including KL-6 and C-reactive protein
- Imaging Session
 - Tumor assessment (to be performed at approximately 4 weeks (Cycle 2, Day 1 [up to Cycle 2, Day 10]), 8 weeks (Cycle 3, Day 1 [up to Cycle 3, Day 10, with at least 28 days from previous tumor assessment]), and approximately every 8 weeks [± 10 days]) thereafter)
 - Whole blood samples (20 mL) on Cycle 2, Day 1, Cycle 3, Day 1, and then every 8 weeks
 - Pulmonary Function Assessment
 - 12-lead ECG prior to that day's patient dose and 1 and 2 hours postdose (**Cycle 2 only**)

- Pharmacokinetic blood sampling (**4 mL**):
 - **Phase 2:** Predose and 1 and 2 hours postdose (± 15 minutes) samples drawn on Cycle 2, Day 1 only and predose on Cycle 3, Day 1 and then every 8 weeks.
- Collect and dispense pozotinib
- Dispense supportive care medications as needed
- Adverse event assessment using NCI CTCAE, Version 5.0
- Concomitant medications
- Patient Diary collected and dispensed

5.3.8 Safety Follow-up/End-of-Study Visit (35 [± 5] Days after Last Dose of Study Treatment)

The **Safety Follow-up Visit** is required 35 (± 5) days after the last dose of pozotinib is administered. The following assessments are to be performed at this visit:

- Weight
- Physical examination
- Vital signs
- Pulmonary Function Assessment and Resting O₂ Saturation
- ECOG Performance Status assessment
- Pregnancy test in women of childbearing potential
- Tumor assessment (unless the patient has documented disease progression or has undergone a tumor assessment within the previous 8 weeks)
- Complete blood count with 5-part differential
- Serum chemistry, including KL-6 and C-reactive protein
- 12-lead ECG
- Newly biopsied tumor tissue taken from patients who progress (optional, but highly encouraged) (**Phase 2 only**)
- Whole blood samples for plasma ctDNA analysis if the patient progresses (optional) (**Phase 2 only**)
- Adverse event assessment using NCI CTCAE, Version 5.0
- Concomitant medications

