5.4.6 Tumor Assessment

Results of standard-of-care tests or examinations performed within 28 days prior to Cycle 1, Day 1 may be used for the Screening/Baseline tumor assessment. Tumor assessments must be performed using computed tomography (CT), positron emission tomography (PET)/CT, or magnetic resonance imaging (MRI). The image will be reviewed by a local radiologist as the Baseline image for response assessment and per the Investigator's standard of care.

For patients with known brain metastases, a Baseline brain MRI scan (within 28 weeks prior to Cycle 1, Day 1) will also be performed to assess the status of brain metastases if present.

Tumor assessments will also be performed at 4 weeks (Cycle 2, Day 1 [up to Cycle 2, Day 10]), 8 weeks (Cycle 3, Day 1 [up to Cycle 3, Day 10, with at least 28 days from previous tumor assessment]), and then every 8 weeks (\pm 10 days) for up to 24 months or until disease progression, death, intolerable adverse events (AEs), or other protocol-specified reasons for patient withdrawal or for a maximum of 24 months.

Tumor assessment will be performed at the Safety Follow up Visit unless the patient has documented disease progression or has undergone a tumor assessment within the previous 8 weeks.

Each subsequent tumor assessment must use the same baseline radiographic technique, either CT, PET/CT, or MRI. Tumor assessments will be made according to RECIST criteria, Version 1.1 [\[22\]](#) using appropriate radiographic imaging or other techniques. For radiographic assessment, CT, PET/CT, or MRI must be performed at every assessment. Patient enrollment and clinical decisions will be based on local review.

Measurable and non-measurable lesions that will not be followed by radiographic methods should be documented appropriately.

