8.5 Efficacy Analyses

Phase 1: No efficacy analyses will be performed in Phase 1.

Phase 2: The primary efficacy variables, as described below, will be summarized and analyzed descriptively, along with 95% CI, for each cohort based on local radiographic review.

- **Objective Response Rate (ORR)** will be assessed according to the Response Evaluation Criteria in Solid Tumors (RECIST) Guidelines, version 1.1 [22] and is defined as the best response [Complete Response (CR) + Partial Response (PR)] recorded from the start of the study until the end of study in patients who received at least 1 dose of pozotinib. The ORR will be based on the Evaluable Population.

The primary endpoint analysis will be performed using point estimate and the 95% CI.

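### Phase 2 efficacy, including the primary ORR, is analysed only in patients who complete a cycle and are RECIST-evaluable, which probably inflates ORR and DCR

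*Combined protocol and SAP*

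**What the plan says.** Section 8.3 and the synopsis define two populations for each cohort.

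- **Evaluable Population:** enrolled Phase 2 patients who "complete at least 1 cycle of pozotinib treatment, and is evaluable for tumor response based on RECIST" criteria (section 8.3 wording; the synopsis matches it). Section 8.3 adds: "The efficacy data will be analyzed using the Evaluable Population".
- **Safety Analysis Population:** everyone who consented, enrolled and took at least one dose. It is assigned only to demographics, baseline characteristics and safety.

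Section 8.5 defines ORR as best response "in patients who received at least 1 dose of pozotinib. The ORR will be based on the Evaluable Population". The first half of that quotation names all dosed patients and the second half names the smaller set. No all-treated efficacy analysis, sensitivity analysis or non-responder rule is given.

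Section 8.5.1 starts PFS at the treatment start date. Section 8.1 plans 20 patients per cohort, expects an ORR of 30%, and states a 95% CI width of 0.424. Replacement of early dropouts is described in the synopsis and section 8.1 for Phase 1, tied to DLT evaluation.

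**The concern.** Membership of the efficacy set depends on what happens after treatment starts. The first scheduled on-treatment scan is at 4 weeks (section 5.4.6), after Cycle 1. A patient who dies, stops for toxicity or clinical progression, or withdraws before then will usually have no documented response. That patient is removed from the denominator and rarely from the numerator, so ORR and DCR tend to rise. PFS is affected too: Cycle 1 deaths, and any later progression or death in an excluded patient, are dropped from a time-to-event measure that is meant to start at first dose.

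ORR is the only primary endpoint of Phase 2. With no formal test, the estimate and its interval are the result. Section 8.1 says the methods follow SPI-POZ-202, whose Cohort 1 result in section 1.2 is reported on an intent-to-treat basis. An evaluable-only ORR would not share that denominator.

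**Working it through.** **Inputs from the documents.** n = 20 per cohort, expected ORR 30%, 95% CI width 0.424 (section 8.1). SPI-POZ-202 Cohort 1: 115 patients, 17 responders and 62 with stable disease, intent-to-treat (section 1.2).

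**Assumed inputs.** The number excluded, k = 1, 2 or 4 of 20. A DCR of 14/20 = 70.0%, chosen to be close to the Cohort 1 figure of (17 + 62)/115 = 68.7%.

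**Step 1: reproduce the planned width.** The exact (Clopper-Pearson) limits for x of n are the 0.025 quantile of Beta(x, n − x + 1) and the 0.975 quantile of Beta(x + 1, n − x). For 6/20 they are 0.1189 and 0.5428, a width of 0.4239, which matches 0.424. Wald (0.402) and Wilson (0.373) intervals do not match. The stated precision is therefore an exact interval with all 20 patients counted. The same method gives 8.9% to 22.6% for 17/115 = 14.8%, as section 1.2 reports.

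**Step 2: exclude k patients who are neither responders nor disease-controlled.** The rate is multiplied by 20/(20 − k).

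| k | ORR (exact 95% CI) | Width | DCR (exact 95% CI) | Width |
|---|---|---|---|---|
| 0 | 6/20 = 30.0% (11.9–54.3) | 0.424 | 14/20 = 70.0% (45.7–88.1) | 0.424 |
| 1 | 6/19 = 31.6% (12.6–56.6) | 0.440 | 14/19 = 73.7% (48.8–90.9) | 0.421 |
| 2 | 6/18 = 33.3% (13.3–59.0) | 0.457 | 14/18 = 77.8% (52.4–93.6) | 0.412 |
| 4 | 6/16 = 37.5% (15.2–64.6) | 0.494 | 14/16 = 87.5% (61.7–98.4) | 0.368 |

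If ORR is held at 30% so that only n changes (beta quantiles with a non-integer count), the widths are 0.435, 0.446 and 0.472 for n = 19, 18 and 16. The DCR interval narrows as the estimate rises, so the inflated figure also looks more precise.

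**Step 3: the opposite direction.** Section 5.4.6 provides that "Tumor assessment will be performed at the Safety Follow up Visit unless the patient has documented disease progression" or a scan within the previous 8 weeks; section 5.3.8 says the same. A Cycle 1 stopper could therefore be scanned, show a partial response or stable disease, and still be excluded for not completing a cycle. Losing one responder gives 5/19 = 26.3% (9.1–51.2). Losing one disease-controlled patient gives 13/19 = 68.4% (43.4–87.4).

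**Step 4: how likely any exclusion is.** The nearest documented figure, from Cohort 1, is: "Permanent drug discontinuation related to AEs was seen in only 10% of patients". That equals 2 of 20. It covers the whole treatment period, and it omits deaths, withdrawals and clinical progression, so it is neither a floor nor a ceiling for Cycle 1 losses. If each patient independently had a 5% to 10% chance of exclusion (assumption), the chance of keeping all 20 in a cohort is 0.95^20 = 0.358 down to 0.90^20 = 0.122.

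**The case against.** - **Evaluable is undefined.** It could mean only measurable disease at baseline, which inclusion criterion 5 already requires. Few patients would then fail that part. The cycle-completion condition still removes Cycle 1 stoppers on any reading.
- **The two sentences in section 8.5 can be reconciled.** Evaluable patients are a subset of dosed patients, so the first sentence may describe the endpoint and the second the analysis set. That is a fair reading. It shows that the restriction is deliberate, and it does not remove the bias.
- **Section 8.4 defers further detail to a SAP.** A later SAP could add sensitivity analyses, but the efficacy set is already fixed in the synopsis, 8.3 and 8.5.
- **Replacement could preserve n = 20.** Sections 3.1.1 and 8.2 contain broader replacement sentences. Both sit in Phase 1 text, and replacing patients would restore precision without removing the selection.
- **The effect is small and no decision rests on it.** This stands in part. At 2 of 20 excluded, the shift is 3.3 points against an interval of 11.9% to 54.3%, and the 4-of-20 case has no support in the documents. Efficacy is called preliminary, and no test or power is specified.
- **The comparison with SPI-POZ-202 is already imperfect.** True: its 14.8% is a confirmed ORR in the EGFR cohort alone, so the denominator is only one of the differences.

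**Conclusion.** The concern holds and should be fixed. The plan restricts the primary ORR and the other Phase 2 efficacy data to a set defined partly by early outcome, and it offers no all-treated analysis alongside. The existence of the restriction is certain. An upward bias in ORR and DCR is likely rather than certain, and its size is unknown because no non-evaluable rate is given. Under the assumed 1 to 4 exclusions per cohort, ORR rises by 1.6 to 7.5 points from 30.0%, and DCR by 3.7 to 17.5 points from 70.0%. The ORR interval widens gradually beyond the planned 0.424. Type I error is not affected, because nothing is tested.

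**What to change.** In the synopsis and sections 8.3 and 8.5:

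1. Make all Phase 2 patients who received at least one dose the primary set for ORR, DCR and PFS, by cohort. This agrees with the dosed-patient wording already in the ORR definition, and it settles the two sentences in 8.5.
2. Count patients with no evaluable post-baseline scan as non-responders and as not disease-controlled.
3. Keep the Evaluable Population as a sensitivity analysis, state what evaluable means, and report the number excluded and the reasons for each cohort.
4. Use the same all-treated set for exploratory overall survival, which also runs from treatment start (section 8.5.2) and would lose early deaths in the same way.

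The cost is protocol and SAP wording only, with no extra patients or scans. The downside is that the reported ORR and DCR may be slightly lower.

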8.4 General Statistical Methods

The Sponsor's Biostatistics and Data Management (BDM) group will be responsible for data management and statistical analysis of this study. All statistical analyses will be performed using SAS for Windows (version 9.3 or higher). Further details of the criteria and conduct of the statistical analyses will be included in the SAP for this study.

Descriptive statistics will be used to describe the recovery of radioactivity and PK parameters. Pharmacokinetic parameters will be computed and analyzed by standard analytical methods.

8.5 Efficacy Analyses

Phase 1: No efficacy analyses will be performed in Phase 1.

Phase 2: The primary efficacy variables, as described below, will be summarized and analyzed descriptively, along with 95% CI, for each cohort based on local radiographic review.

- **Objective Response Rate (ORR)** will be assessed according to the Response Evaluation Criteria in Solid Tumors (RECIST) Guidelines, version 1.1 [22] and is defined as the best response [Complete Response (CR) + Partial Response (PR)] recorded from the start of the study until the end of study in patients who received at least 1 dose of pozotinib. The ORR will be based on the Evaluable Population.

The primary endpoint analysis will be performed using point estimate and the 95% CI.

8.5.1 Secondary Endpoints

- **DCR**, including CR, PR, and Stable Disease (SD), will be assessed using RECIST, version 1.1 and defined as the proportion of subjects who achieve CR, PR, and SD by the best response from the first dose of pozotinib to the end of study.
- **DoR** will be measured from the date that measurement criteria are first met for CR or PR (whichever status is recorded first) until the first subsequent date that progressive disease or death is documented.
- **PFS** is defined as the number of days from the treatment start date to the date of documented disease progression or death due to any cause. Disease progression will be determined by RECIST Version 1.1.

DCR, DoR, and PFS will be analyzed using descriptive statistics, for each cohort, and with 95% CI for DCR and Kaplan-Meier plot for DoR and PFS.

8.5.2 Exploratory Endpoints

- **Overall Survival** is defined as the number of days from the treatment start date to the date of death due to any cause. After study drug discontinuation, patients who have consented will be contacted every 3 months, for up to 2 years after patient's first dose of pozotinib, for survival assessment.

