2.3 Exploratory Objective

- **Overall Survival**

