3.1.2 Phase 2: Efficacy

Once the MTD/MAD is determined, 40 additional NSCLC patients with EGFR (20 patients) or HER2 (20 patients) exon 20 insertion mutations (including duplication mutations) will be enrolled to evaluate the efficacy of pozotinib at the dose and regimen determined in Phase 1. The choice of QD or BID for Phase 2 will be determined by the sponsor when Phase 1 of the study is complete. If the patient is EGFR positive, then they go in the EGFR group. If the patient is HER2 positive, then they go in the HER2 group. Dose modifications are permitted based on Sponsor recommendations and notification of the Medical Monitor.

[figure not shown]
During each 28-day cycle, patients who are eligible for participation will receive pozotinib at the assigned dose, orally, QD or BID depending on the dosing group, continuously. All patients will be treated for up to 24 months or until disease progression, death, intolerable adverse events (AEs), or other protocol-specified reasons for patient withdrawal. The study design diagram is presented in [Figure 11](#), the dose-finding diagrams are presented in [Figure 12](#), and the schedule of study assessments and procedures is presented in [Appendix 1](#) for Phase 1 and in [Appendix 2](#) for Phase 2.

Figure 11 Study Design Diagram

Note: Phase 2 will start once the dose and dosing schedule have been determined in Phase 1.

Figure 12 Dose-Finding Diagram

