Appendix 1 PHASE 1 SCHEDULE OF ASSESSMENTS AND PROCEDURES

Phase 1 Assessment	Screening	Treatment Period ^a (Each Cycle=28 [\pm 3] Days)						Safety Follow-up /End-of-Study Visit	Long-Term Follow-up Every 3 months After Discontinuation	
		Cycle 1				Cycle 2+				
	Day -30 to Day-1	Day				Day (\pm 2 days)		35 (\pm 5) Days After Last Dose		
		1	7	13	14	22	1			
		Hospitalization								
Informed Consent	X									
Relevant Medical History	X									
Demographic Data	X									
Height and Weight ^b	X	X					X		X	
Physical Examination ^c	X	X	X		X		X		X	
Vital signs ^d	X	X	X		X		X		X	
Resting O ₂ Saturation ^e	X		Daily				X		X	
Pulmonary Function ^f	X	X	X		X		X		X	
ECOG Performance Status ^g	X	X	X		X		X		X	
Pregnancy Test ^h	X	X					X		X	
Hepatitis B Surface Antigen Test ⁱ	X									
Hepatitis B Core Antibody Test ⁱ	X									
Hepatitis B Surface Antibody Test ⁱ	X									
Hepatitis C Antibody Test ^j	X									
HIV Antibody Test ^k	X									
Tumor Assessment ^l	X						X		X	
Whole Blood (metabolic profile) ^m	X									
CBC with 5-part differential and platelets ⁿ	X	X	X		X		X		X	
Serum Chemistry, including KL-6 and C-reactive protein ^o	X	X	X		X		X		X	
Electrocardiogram ^p	X	X	X		X		X ^p		X	
Echocardiogram or MUGA Scan ^q	X									
PK Blood Samples ^r		X		X						
Dispense Pozotinib ^s			Daily				X			
Dispense Supportive Care Medications, as needed			Daily				X			
Adverse Event Assessment ^t	X		Daily				X		X	
Concomitant Medications	X	X	X		X		X		X	

Phase 1 Assessment	Screening	Treatment Period ^a (Each Cycle=28 [±3] Days)						Safety Follow-up /End-of-Study Visit	Long-Term Follow-up
		Cycle 1				Cycle 2+			
	Day -30 to Day-1	Day				Day (±2 days)		35 (±5) Days After Last Dose	Every 3 months After Discontinuation
		1	7	13	14	22	1		
		Hospitalization							
Patient Diary Dispensed/Collected					x		x	x	
Telephone Contact ^u						x		x	x

- a) Patients must visit the site at the beginning of each cycle.
- b) Height only needs to be recorded during the Screening Visit.
- c) A complete physical examination, including auscultation, is required at Screening, Day 1 of each cycle, and at the Safety Follow-up Visit. Symptom-directed exams are required at other visits. In addition, a physical examination will be done on Days 7 and 14 of Cycle 1, while the patient is in the hospital.

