- s) Pozotinib will be dispensed on Day 1 of each cycle. Pozotinib should be taken with food and a glass of water (approximately 240 mL) at approximately the same time(s) each day.
- t) During the Screening Period, only SAEs will be recorded. All AEs will be collected from Cycle 1, Day 1 through the Safety Follow-up Visit. Patients will be hospitalized during the first 2 weeks of the study and will be monitored for safety assessments including AEs, vital signs, ECGs on Day 7 and Day 14 of Cycle 1. Adverse events will be assessed daily while hospitalized.
- u) Telephone contact for AE and concomitant medication assessment on Cycle 1, Day 22 (± 2 days), weekly during Cycle 2 and then Day 15 (± 2 days) in subsequent cycles. During the long-term follow-up patients will be contacted every 3 months to assess survival.

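### Phase 2 survival contacts are timed from drug discontinuation but end 2 years after first dose, with no closing contact, so survival status just before month 24 is incomplete

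*Combined protocol and SAP*

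**What the plan says.** - **Endpoint.** OS is listed under "2.3 Exploratory Objective". Section 8.5.2 says that it "is defined as the number of days from the treatment start date to the date of death due to any cause". No landmark time is named.
- **Contacts.** The same section says that after drug discontinuation "patients who have consented will be contacted every 3 months, for up to 2 years after" the first dose. Sections 3.2, 4.3 and 5.3.9 repeat the 2-year limit from first dose.
- **Schedule.** The long-term follow-up column is headed "Every 3 months After Discontinuation", and the footnote adds: "During the long-term follow-up patients will be contacted every 3 months to assess survival". Both quotes are from Appendix 1 (Phase 1). Appendix 2 (Phase 2) has the same column heading, and its footnote x has the same sentence.
- **Other dates on which a patient is known alive.** Section 3.1.2: "All patients will be treated for up to 24 months or until disease progression". Section 5.3.8: "The Safety Follow-up Visit is required 35 (± 5) days after the last dose of pozotinib is administered".
- **Analysis.** Section 8.5.1 plans its secondary endpoints "with 95% CI for DCR and Kaplan-Meier plot for DoR and PFS". Section 8 gives no method and no censoring rule for OS; Section 8.4 leaves further detail to a SAP. Section 8.5 plans no efficacy analysis in Phase 1, so the point concerns Phase 2.

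**The concern.** Two clocks are in use. OS and the end of follow-up run from first dose, while the 3-month interval runs from the last dose, which differs by patient. The two agree at month 24 only by chance.

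Follow-up to 2 years is the protocol's own limit, so an OS curve would naturally be drawn that far. Over its last 3 months, patients would drop out of the risk set at scattered times set by when they stopped drug. A death after the last contact may or may not reach the site. If it does and is counted, while survivors are censored at their last contact, the end of the curve is pulled down. Status that was never collected cannot be restored at analysis.

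**Working it through.** **Plan's own figures.** None is given for OS. The only precision figure is the 95% CI width of 0.424 for an ORR of 30% with n = 20 (Section 8.1). The exact interval for 6/20 is 0.119 to 0.543, width 0.424, so it reproduces. It sets the scale: cohorts of 20, with no hypothesis test.

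**Gap for one patient.** For discontinuation at month t ≤ 21:

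- number of scheduled contacts = floor((24 − t)/3)
- gap from last contact to month 24 = (24 − t) mod 3

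Stopping at month 5.5 gives a last contact at 23.5 (gap 0.5). Stopping at month 4 gives 22 (gap 2). Stopping at month 3.5 gives 21.5 (gap 2.5). The maximum is just under 3 months.

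**Late stoppers.** After month 21 no 3-monthly contact falls due by month 24, but the Safety Follow-up Visit at 35 days (about 1.15 months) still gives a date. Stopping just after month 21 puts that visit near month 22.15, a gap of about 1.9 months. Stopping from about month 22.9 puts it at or beyond month 24, with no gap. Section 4.3 allows an earlier visit if a new treatment starts, which would lengthen the gap.

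**Assumptions for the cohort calculation.** The documents give neither OS nor time to discontinuation for this trial.

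- OS is exponential with median 12 to 18 months.
- Time to discontinuation is exponential with median 2.7, 5.5 or 8 months. The 2.7 is borrowed from the median PFS by independent review in the earlier study of Section 1.1.3.1, in a different NSCLC population.
- The two times are independent, which is a simplification.
- Contacts are made on time, and deaths on drug are known.

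**Simulated gap** (patients alive and off drug at month 24; OS medians from 10 to 20 months also tried). The mean is 1.6–1.7 months and the median 1.6–1.8. The gap exceeds 1 month in 69–75% and 2 months in 36–42%. Between 0.2% and 13% of 24-month survivors are still on drug and have no gap.

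**At risk at month 23.** Alive: 20 × 2^(−23/12) = 5.3 to 20 × 2^(−23/18) = 8.2. Still at risk under the schedule: about 1.3 to 3.4. Most of the difference is censoring by the schedule. Deaths after the last contact but before month 24 number about 0.4–0.5 per cohort of 20.

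**Precision at month 24.** With complete status, SD = √(p(1 − p)/20). At median OS 15 months, p = 2^(−24/15) = 0.33 and SD = √(0.33 × 0.67/20) = 0.105. Simulated with a 5.5-month median to discontinuation, the SD is 0.116 under the schedule against 0.104 with complete status, a ratio of 1.12. Across the scenarios the excess is about 10–15%.

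**Bias at month 24**, by the share of deaths after the last contact that the site hears of and counts, with survivors censored at last contact:

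| Share counted | Error in the 24-month estimate |
|---|---|
| None | about 0.01 or less |
| Half | about 0.02 to 0.045 too low |
| All | about 0.04 to 0.09 too low |

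Crediting the Safety Follow-up Visit changes little: the largest error becomes about 0.08. The share is unknown, so the range from none to all has to be shown.

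**Up to month 21.** Every patient who stops by month 21 has a last contact after month 21, and later stoppers are on drug then. Estimates to month 21 are therefore unaffected if contacts are on time.

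**The case against.** The strongest objection is that no planned analysis is harmed. A reader might infer that a planned 24-month OS rate loses its support. The documents do not bear that out: OS is the sole exploratory objective, no landmark is named, Kaplan-Meier plots are specified for DoR and PFS only, and the limit is worded as a maximum, not as a time of analysis. That part stands.

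A reader might also infer that OS will be biased downward. The documents do not establish this either. They give no OS censoring rule, and under ordinary censoring with no late deaths counted the error is about 0.01 or less. The downward bias is conditional on late deaths being captured selectively.

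Third, under an assumed median OS of 12 to 18 months, 6 to 9 of 20 patients are alive at month 21, and it is tempting to read that as the loss. It is only the number who could be affected; the deaths that go unseen are about 0.4–0.5 per cohort. Cohort size dominates precision, since the SD is already about 0.10 to 0.11 with complete status.

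Finally, the wording does not forbid a contact at month 24, and the Safety Follow-up Visit covers part of the gap for late stoppers. Both are true. But the wording does not require such a contact either, and most off-drug survivors stopped long before month 21.

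**Conclusion.** The scheduling fault is real and its consequence small. In Phase 2, survival status is incomplete over the last 0 to 3 months (typically about 1.6) before the protocol's own 2-year limit for most patients alive and off drug. Under the stated assumptions about 1 to 4 of 20 per cohort remain at risk at month 23. A 24-month Kaplan-Meier estimate would have an SD about 10–15% larger than necessary. Its error would run from about 0.01 or less to 0.02–0.09 too low, depending on how many late deaths are counted.

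The gap follows from the text alone. The cohort figures rest on assumed exponential and independent times, with medians that the documents do not supply. This is a cheap improvement to an exploratory endpoint and does not touch the primary analysis.

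**What to change.** For Phase 2, make one of two changes in Sections 8.5.2, 5.3.9 and 4.3 and in footnote x of Appendix 2:

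- Add one survival-status contact at 24 months (±2 weeks) after first dose for every consenting patient not known to have died, including those who stop drug after month 21. Word the 2-year limit so that it admits this window.
- Or anchor the 3-monthly contacts to first dose (months 3, 6, … 24) and change the Appendix 2 column heading to match.

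Keep the synopsis and Section 3.2, which repeat the sentence, in step. The Phase 1 footnote need not change for efficacy purposes.

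The cost is a small wording change and at most one extra telephone contact per surviving patient. Re-anchoring keeps the frequency and needs about the same number of calls. The change has to be made prospectively: a censoring rule in the SAP could limit the bias but would not recover unknown status.
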